### **8. PARTICIPANT COMPLETION AND WITHDRAWAL**

#### **8.1 Participant completion**

A participant who returns for the concluding visit/is available for the concluding contact foreseen in the protocol is considered to have completed the study.

#### **8.2 Participant withdrawal**

Participants who are withdrawn because of SAEs/AEs must be clearly distinguished from participants who are withdrawn for other reasons. Investigators will follow participants who are withdrawn as result of a SAE/AE until resolution of the event. Withdrawals will not be replaced, unless the withdrawal is prior to the first dose of study vaccine.

#### **Participant withdrawal from the study**

From an analysis perspective, a ‘withdrawal’ from the study refers to any participant who did not come back for the concluding visit/was not available for the concluding contact foreseen in the protocol.

All data collected until the date of withdrawal/last contact of the participant will be used for the analysis.

A participant is considered a ‘withdrawal’ from the study when no study procedure has occurred, no participant contact has been performed and no further information has been collected for this participant from the date of withdrawal/last contact.

Investigators will make an attempt to contact those participants who do not return for scheduled visits or participant contact.

Information relative to the withdrawal will be documented in the eCRF. The investigator will document whether the decision to withdraw a participant from the study was made by the participant, or by the investigator, as well as which of the following possible reasons was responsible for withdrawal:

- SAE
- Non-serious AE
- Protocol violation (specify)
- Consent withdrawal, not due to an AE\*
- Moved from the study area.
- Lost to participant contact.
- Other (specify).

*\*In case a participant is withdrawn from the study because he/she has withdrawn consent, the investigator will document the reason for withdrawal of consent, if specified by the participant, in the eCRF.*

Participants who are withdrawn from the study because of SAEs/AEs must be clearly distinguished from participants who are withdrawn for other reasons. Investigators will follow participants who are withdrawn from the study as result of a SAE/AE until resolution of the event.

### **Participant withdrawal from investigational product**

A ‘withdrawal’ from the investigational product refers to any participant who does not receive the complete treatment, i.e. when no further planned dose is administered from the date of withdrawal. A participant withdrawn from the investigational product may not necessarily be withdrawn from the study as further study procedures or participant contact may be performed (safety or immunogenicity) if planned in the study protocol.

Information relative to premature discontinuation of the investigational product will be documented on the Product Administration screen of the eCRF. The investigator will document whether the decision to discontinue further injection/treatment was made by the participant, or by the investigator, as well as which of the following possible reasons was responsible for withdrawal:

- SAE
- Non-serious AE
- Other (specify)

## 9. OUTCOME MEASURES AND STATISTICAL METHODS

### 9.1 Sample Size Estimation

Since this is an open, non-comparative study that seeks to observe the impact of vaccination on the evolution of HIV disease, a sample size defined by statistical criteria is not established.

### 9.2 Study Population and Analysis Sets

#### 9.2.1 Study Population

##### Intent-to-Treat Cohort

The intent-to-treat cohort consists of all participants who receive at least one study injection, regardless of their protocol adherence and continued participation in the study. Participants will be analyzed according to their randomized treatment. Participants who withdraw from the study will be included up to the date of their study withdrawal.

##### Per-protocol Analysis Cohort

The per-protocol analysis cohort for safety includes subjects in the intent-to-treat who receive the correct treatment, the correct number of doses, and who do not have a major protocol deviation. Detailed definition of this analysis set including definition of major protocol deviations will be described in the Statistical Analysis Plan. The per-protocol analysis cohort for immunogenicity includes subjects in the per-protocol analysis cohort for safety whose samples were drawn inside of protocol specified time windows.

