Participants will be provided with access to an e-diary or a paper diary card and a thermometer, and instructions about how to use them. The use of an e-diary instead of a paper diary card is dependent on the study site. Participants will be asked to record solicited AE for 7 days after receiving the vaccination, and unsolicited AE for 28 days, in their diary. The completed e-diary and diary cards will be reviewed, and data collected at the 28-Day safety in-person visit. A new diary will be provided at Day 56 and collected at Day 84. Non completion of the e-diary or diary cards will be investigated with the participant through telephone call(s) or any other convenient procedure. All data collected from the e-diary and diary cards will be uploaded into the eCRF.

- **Efficacy participant contacts**

All participants will have efficacy participant contacts weekly for 52 weeks following vaccination. There will be approximately 52 electronic efficacy participant contacts. All efficacy participant contacts will be text messages, although other electronic method such as by phone, e-mail, the Internet is suitable, if preferred. Each participant contact needs to be recorded in the study electronic case report form. The purpose of these participant contacts is to serve as a reminder to participants to report any symptoms of illness they may be experiencing, regardless of severity. Any possible COVID-19 relevant symptoms (e.g., fever, cough, shortness of breath, etc., according to WHO case definitions; see Section 3.8) will trigger laboratory testing for SARS-CoV-2 infection.

- **Illness participant contact visits (Confirmed or suspected infection during study)**

Participants will be provided detailed instructions regarding the signs and symptoms of COVID-19 disease at each participant contact and will be instructed to seek medical attention and notify study staff should symptoms occur filling the illness visit form and completing the eCRF. The form should be updated and sent and sent when the case meets the definition of severe COVID, and when the case resolves. Symptoms of concern include cough, fever, diarrhea, prolonged fatigue, respiratory symptoms, pneumonia, difficulty swallowing, loss of sense of smell and neurological events. For symptoms of interest, please refer to 3.8 efficacy participant contact.

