# 6. STUDY PRODUCT AND ADMINISTRATION

## 6.1 Description of Study Product

Recombinant Novel Coronavirus Vaccine (Adenovirus Type 5 Vector). This vaccine, Ad5-nCoV, is a replication-defective recombinant human type 5 adenovirus expressing novel coronavirus S protein, which is produced by viral amplification in HEK293SF-3F6 cells, purification and formulation with addition of proper excipients. The product is used for prevention from infection caused by novel coronavirus.

**Active Ingredients:** Replication-defective recombinant human type 5 adenovirus expressing S protein of novel coronavirus

**Excipients:** Mannitol, sucrose, sodium chloride, magnesium chloride, polysorbate 80, HEPES, and glycerin

**Packaging:** The vaccine is contained in a vial.

**Specification:** 0.5 mL/vial

**Dosage**  $5 \times 10^{10}$  vp ( $\geq 4 \times 10^{10}$  vp)

\* Explanatory note: The vials contain a volume of 0.5 ml. The indication is to administer this amount. The manufacturer of the vaccine has advised that a volume between 0.4 ml and 0.5 ml per dose is permitted since it has been calculated that the 0.4 ml extractable volume of each vial in the lot involved in this study (Lot NCOV202103006) has met the requirements of the study based on good vaccination practices. The vaccines used in this study have passed the quality control procedure during the filling process and the fill volume of the vaccines meets the quality standards.

**Shelf Life:** Tentatively 24 months

**Storage:** This vaccine should be stored and transported at 2-8°C.

**Administration:** Intramuscular injection in the deltoid muscle of the upper arm.

**Schedule:** A double-dose of active vaccine is planned for all participants. A second dose of active vaccine is planned for all participants 56 days after the first Injection.

**Manufacturer:** CanSino Biologics Inc.  
[name]  
Postal code: 300462  
[contact]  
[contact]  
Website: [www.cansinotech.com](http://www.cansinotech.com)

**Developers:** CanSino Biologics Inc.  
Beijing Institute of Biotechnology

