### Contraindications to administration of the study product at Day 56 Second Injection Day

- Acute disease and/or fever at the time of administration.
- Suspicion of COVID19 case due to symptoms.
- Fever ( $\geq 39.0^{\circ}\text{C}$ ) lasting at least 72 hs after the first injection.
- Adverse events related to the study product (severe or serious).

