**Assessment of adverse events****Assessment of intensity**

The intensity of the following solicited AEs will be assessed as described:

The maximum intensity of local injection site redness/swelling will be scored as follows:

0: ≤ 20 mm

1: > 20 - ≤ 50 mm

2: > 50 - ≤ 100 mm

3: > 100 mm

The grade of fever will be scored as follows (oral temperatures\*):

1: ≥ 38.0°C (100.4°F) - ≤ 38.5°C (101.3°F)

2: > 38.5°C (101.3°F) - ≤ 39.0°C (102.2°F)

3: > 39.0°C (102.2°F) - ≤ 40.0°C (104°F)

4: > 40.0°C (104°F)

\*oral temperature=axillary temperature+0.2°C

The investigator will assess the maximum intensity that occurred over the duration of the event for all unsolicited AEs (including SAEs) recorded during the study. The assessment will be based on the investigator's clinical judgment.

The intensity should be assigned to one of the following categories:

- Grade 1 (mild) = An AE which is easily tolerated by the participant, causing minimal discomfort and not interfering with everyday activities.
- Grade 2 (moderate) = An AE which is sufficiently discomforting to interfere with normal everyday activities.
- Grade 3 (severe) = An AE which prevents normal, everyday activities
- Grade 4= An adverse event that is potentially life threatening.
- Grade 5=An AE which results in death.

An AE that is assessed as Grade 3 (severe) should not be confused with a SAE. Grade 3 is a category used for rating the intensity of an event; and both AEs and SAEs can be assessed as Grade 3. An event is defined as 'serious' when it meets one of the predefined outcomes.

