### **Assessment of causality**

The investigator is obligated to assess the relationship between investigational product and the occurrence of each AE/SAE. The investigator will use clinical judgment to determine the relationship. Alternative plausible causes, such as natural history of the underlying diseases, concomitant therapy, other risk factors, and the temporal relationship of the event to the investigational product will be considered and investigated. The investigator will also consult the IB and/or PI to determine his/her assessment.

There may be situations when a SAE has occurred, but the investigator has minimal information to include in the initial SAE report. However, it is very important that the investigator always assesses causality for every event prior to submission of the SAE report. The investigator may change his/her opinion of causality in light of participant contact information and update the SAE information accordingly. The causality assessment is one of the criteria used when determining regulatory reporting requirements.

In case of concomitant administration of multiple products, it may not be possible to determine the causal relationship of general AEs to the individual products administered. The investigator should, therefore, assess whether the AE could be causally related to injection rather than to the individual products.

All solicited local (injection site) reactions will be considered causally related to injection. Causality of all other AEs should be assessed by the investigator using the following question:

*Is there a reasonable possibility that the AE may have been caused by the investigational product?*

**YES:** There is a reasonable possibility that the product(s) contributed to the AE.

**NO:** There is no reasonable possibility that the AE is causally related to the administration of the study product(s). There are other, more likely causes and administration of the study product(s) is not suspected to have contributed to the AE.

If an event meets the criteria to be determined as 'serious', additional examinations/tests will be performed by the investigator in order to determine ALL possible contributing factors for each SAE.

Possible contributing factors include:

- Medical history.
- Other medication.
- Protocol-required procedure.
- Other procedure not required by the protocol.
- Lack of efficacy of the product, if applicable.
- Erroneous administration.
- Other cause (specify).

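### The per-protocol safety cohort loses participants whose second dose is withheld because of an adverse event, so this second safety analysis understates those events after dose 1

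*Protocol*

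**What the plan says.** Section 9.2.1 defines the cohort by dose count: "The per-protocol analysis cohort for safety includes subjects in the intent-to-treat who receive the correct treatment, the correct number of doses". It adds that there must be no major protocol deviation, and leaves the detailed definition to the SAP.

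Section 6.1 fixes how many doses are intended: "A second dose of active vaccine is planned for all participants 56 days after the first Injection". Section 8.2 treats as withdrawn from the product "any participant who does not receive the complete treatment, i.e. when no further planned dose is administered".

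Section 6.2, in the list for the Day 56 injection, names as contraindications "Adverse events related to the study product (severe or serious" and fever of at least 39.0 °C "lasting at least 72 hs after the first injection". The corresponding list for the first injection allows injection at a later date; the Day 56 list has no such sentence.

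Section 9.3.3 closes by basing the safety analysis on both the intent-to-treat and the per-protocol cohorts, and does not rank them. Intent-to-treat (9.2.1) keeps everyone with at least one injection. The synopsis states that the primary safety endpoint uses data from all participants.

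**The concern.** Membership of a safety analysis set should not depend on the safety outcome that the set reports. Here it does. A listed event after dose 1 can stop dose 2, the missing dose 2 removes the participant, and the event goes with the participant.

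The per-protocol tables would then show few or no related severe or serious dose-1 events for a reason unrelated to the vaccine's tolerability. Safety is a primary objective (section 2.1), and section 1.3 gives the trial's purpose as collecting enough safety data to support use in people with HIV. A reader who took the per-protocol rows as confirming the intent-to-treat rows would be misled.

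**Working it through.** The protocol states no rate for these events and no figure for this cohort, so there is nothing to reproduce. The check has three parts.

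**1. Are the events known before the second dose?** Section 5.1 says of the dose-1 diary: "The completed e-diary and diary cards will be reviewed, and data collected at the 28-Day safety in-person visit". Table 1 allows ±7 days at Day 28 and at Day 56. The latest review is Day 28 + 7 = Day 35, and the earliest second injection is Day 56 − 7 = Day 49. Diary review therefore comes at least 49 − 35 = 14 days before the second dose.

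Relatedness is automatic for one group of events: "All solicited local (injection site) reactions will be considered causally related to injection". Other events need the investigator's causality judgement, except the prolonged-fever criterion, which does not mention causality.

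**2. What does the exclusion do to the rate?** Let N = 500 be vaccinated, k have a listed event after dose 1, and m of those k still receive dose 2 and stay in the cohort. With no other exclusions:

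- all dose-1 recipients: k / N
- per-protocol: m / (N − (k − m))

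| Assumed k | All recipients | None dosed | Some dosed | Half dosed |
|---|---|---|---|---|
| 4 | 4/500 = 0.80% | 0/496 | m = 1: 1/497 = 0.20% | m = 2: 2/498 = 0.40% |
| 10 | 10/500 = 2.0% | 0/490 | m = 2: 2/492 = 0.41% | m = 5: 5/495 = 1.01% |
| 15 | 15/500 = 3.0% | 0/485 | m = 3: 3/488 = 0.61% | not a whole number |

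Because N is large compared with k, the ratio of the two rates is close to m/k. The understatement is about five-fold if a fifth are dosed and about two-fold if half are; these factors restate the assumed retention and are not a separate result. With none dosed, 0/490 has an exact 95% upper limit of 0.75%, which looks precise but is produced by the selection.

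**3. Where do the assumed rates come from?** The low end uses the phase II trial in healthy adults described in section 1.2: 508 randomised 2:1:1, Grade 3 reactions in 9% at the higher dose, and p = 0.0011 against the present dose. If the split was exactly 254/127/127, Fisher's exact test on 22/254 against 1/127 gives p = 0.0011. That fits about 1/127 = 0.8%, or 4 in 500. One event in 127 has an exact 95% interval of 0.02% to 4.3%, so the anchor is loose. The 2% and 3% rates are illustrations with no source in the protocol.

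Common reactions barely move. With 56% injection-site pain (section 1.2), and every excluded participant assumed to have had pain, 280/500 = 56.0% becomes 276/496 = 55.6% with 4 excluded, or 265/485 = 54.6% with 15 excluded.

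**The case against.** **The main safety results are intact.** This stands. Intent-to-treat keeps everyone injected, the synopsis uses all participants for the primary safety endpoint, section 9.3.3 lists all SAEs, and the synopsis lists all SAEs and MAEs. A reader might infer that the trial's safety results as a whole hide severe events; the protocol does not support that. Per-protocol safety also rests on the 9.2.1 definition and one sentence in 9.3.3, since the synopsis asks for per-protocol analysis only for immunogenicity.

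**The definition is left to the SAP.** This stands in part. The SAP could read the dose-count phrase by dose period, or class a dose withheld under section 6.2 as correct. But the protocol itself writes the dose-count condition, and nothing in it makes that allowance.

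**Section 6.2 does not say that a resolved event bars the second dose.** This stands. The related-event line carries no time qualifier, whereas the fever line refers to the period after the first injection and the acute-illness line to the time of administration. A reader might infer that the per-protocol count must be zero whatever the true rate. That follows only if section 6.2 is applied to every such event known before Day 56, resolved or not. If only ongoing events count, many short-lived reactions would stay in. Events reported late, or judged related after Day 56, can also stay in. On the other hand, the SAP might class dosing against a contraindication as a major deviation, which would remove those participants again.

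**The case is not tight for local reactions.** This stands in part. The definition "Grade 3 (severe) = An AE which prevents normal, everyday activities" belongs to the scale introduced for unsolicited events, while redness and swelling are scored by diameter. The most common Grade 3 reaction in the phase II trial was fever, which is not automatically counted as related. Severe solicited local reactions may therefore be a minority of the affected events.

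**Conclusion.** The point holds in a limited form. As written, the dose-count condition in 9.2.1 and the second-dose contraindications in 6.2 make membership of the per-protocol safety cohort depend on the outcome. The per-protocol analysis in 9.3.3 therefore understates related severe or serious events, and prolonged high fever, after dose 1.

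The direction needs no assumed rate; it needs only that some second doses are withheld for these events. The size does rest on assumptions: the event rate, the share still dosed, and a SAP that does not soften the dose-count condition. The harm is confined to the per-protocol safety tables. It is worth correcting because safety is a primary objective and the correction is easy, but no primary result is put in doubt.

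**What to change.** In 9.2.1 and 9.3.3, state that safety is based primarily on all participants with at least one Ad5-nCoV dose. Use dose-1 recipients as the denominator for events after dose 1, and dose-2 recipients for events after dose 2.

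Then either drop the per-protocol safety analysis, or label it supportive and state that a second dose withheld because of an adverse event does not exclude a participant.

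The cost is one or two sentences in each section. No new data are needed, trial conduct does not change, and no change to the dosing rule is proposed.

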### 9.3 Statistical Analysis

This purpose of this section is to describe various planned analyses in this study. Details of statistical methods will be included in the Statistical Analysis Plan, which will be finalized prior to the first interim analysis.

#### 9.3.1 Demographics and Baseline Characteristics

Demographic and baseline characteristics will be summarized overall and then by treatment group using appropriate descriptive statistics. Continuous data will be summarized using the number of observations, mean, standard deviation, median, minimum and maximum. Categorical data will be summarized using frequency counts and percentages. 95% confidence intervals will be reported, but no statistical hypothesis testing will be conducted. Results will be presented for all participants.

#### 9.3.2 Efficacy Analysis

Due to limited sample size, no formal efficacy hypothesis will be tested. A listing of baseline characteristics, treatment group and outcome for virologically confirmed (PCR positive) serologically confirmed COVID-19 cases will be produced. An exploratory efficacy analysis of

Ad5-nCoV in preventing asymptomatic disease of COVID-19 will also be conducted at the end of the study.

### **9.3.3 Safety Analysis**

#### **Primary Safety Endpoint:**

- The incidence of solicited adverse reactions within 7 days after vaccination.
- The incidence of unsolicited adverse events within 28 days after vaccination.
- The incidence of detectable viral load 24 and 52 weeks after vaccination
- The incidence of serious adverse events (SAE) and medically attended adverse events (MAE) within 52 weeks after vaccination in all participants.

